Genesis NICU is a Level II Regional Neonatology Center staffed full time by neonatologists from the University of Iowa Children's Hospital. The Genesis NICU provides family-centered treatment for babies born as early as 30 weeks gestation.

Participant Selection and Recruitment

The study will include 150 participants. There are no existing studies examining the time to diaper dermatitis for any treatment options (coconut oil or others), therefore, we conducted the simulation below to estimate a sample size that will have enough power to measure the primary outcomes in the study. The simulation generated time to discharge from a Gamma (3,2) and time to rash for coconut oil of Gamma (2,2) and standard Gamma (3,2). Patients that were discharged before getting diaper dermatitis were censored.

75 each Treatment: Gamma Scale 2 vs. 3, Shape = 2, p-value = 0.002.

The inclusion/exclusion criteria for the study is outlined below:

1. Inclusion criteria:
 - a. Babies admitted to the Genesis NICU
 - b. Anticipated stay in the NICU is ≥ 48 hours
 - c. Babies wearing diapers 24 hours a day
 - d. Parent willing to sign informed consent for the study
 - e. Parent willing to use the test products in the diaper area during the trial
 - f. Parent willing to not change the type or brand of diaper and wipes during the study
 - g. Parent willing to refrain from changing any other products whose use may have an effect of their baby's skin condition during the trial

2. Exclusion criteria:

- a. Babies with a gestational age <30 weeks
- b. Babies with major congenital malformations
- c. Active dermatological conditions other than diaper dermatitis that may affect trial results
- d. Known sensitivity to ingredients in trial products
- e. Babies whose parents have a hazelnut or coconut allergy
- f. Babies whose mother is <18 years of age
- g. Other severe acute medical conditions that may increase the risk associated with trial participation

3. Recruitment

[figure not shown]

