Participants meeting the inclusion/exclusion criteria that consent to participate in the study will be randomized to one of two Study Arms: Coconut Oil or Standard of Care. The Genesis Business Intelligence Unit will utilize block randomization (blocks of 5) to create 200 cards (50 extra to allow for potential participant attrition) that will include the randomized study arm and a randomly assigned patient number. These cards will be placed in a security envelope and stored in the Research office. Upon receipt of an informed consent, a Clinical Research Coordinator will draw an envelope in sequential order and will notify the participant's parents of his/her study arm. The Clinical Research Coordinator will also place the correct treatment (i.e., coconut oil or standard of care) in the participant's room and will notify the charge nurse in the NICU of the participant's study arm. The Clinical Research Coordinator will use a Randomization Log to record the participant's name, birthdate, study number, study arm and coordinator initials. This log will be kept confidential and secured throughout the study period in the locked Research office.

Participants in each arm will be cleaned with the same Pampers Sensitive brand wipes and will receive the same Pampers brand disposable diaper. The Coconut Oil group will receive coconut oil at each diaper change. An individual sterilized container of unrefined, organic coconut oil will be placed in the participant's room. The coconut oil will be obtained from a large jar and will be placed into the individual sterilized container at the time of randomization. The coconut oil will be labeled with the participant's name and date of birth. At each diaper change participants will

be cleaned with Pampers brand wipes and a generous layer of coconut oil will be applied to the diaper area, including buttocks and creases between thighs and hips. Participants in the Coconut Oil group that develop diaper dermatitis will continue to use coconut oil until they are discharged or reach the primary safety endpoint. They will also be switched from using Pampers Sensitive wipes to a dry washcloth and water, per the standard of care.

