The Standard of Care group will receive the current standard of care for diaper dermatitis. The standard of care is no treatment until a diaper dermatitis appears. If diaper dermatitis appears, participants will receive a generous layer of Medline Remedy Phytoplex Z-Guard Skin Protectant, which is an over-the-counter skin protectant with the following active ingredients: white petrolatum 57% and zinc oxide 17%. The participants will also be switched from using Pampers Sensitive wipes to a dry washcloth and water, per the standard of care.

The primary safety endpoint for this study will be skin that is eroded and/or blistered in the diaper area with bleeding. If a participant reaches the primary safety endpoint their study participation will be complete and additional diaper dermatitis treatment options can be used, per currently available treatment options in the Genesis NICU.

The research staff will conduct a quality check each week using a sample of participant rooms to ensure the participants continue to receive care based on the study arm they were assigned to and the diaper dermatitis logs are being completed for every diaper change.

Study Outcomes

Primary Outcomes:

1. The number of days free from diaper dermatitis, as measured by the diaper dermatitis log.
2. The number of participants that develop adverse effects.

Secondary Outcomes:

3. For participants that develop diaper dermatitis, the number of days with diaper dermatitis (duration of diaper dermatitis).
4. For participants that develop diaper dermatitis, the number of days until the participant reaches the primary endpoint (skin eroded and/or blistered with bleeding), as measured by the diaper dermatitis log.
5. The level of parent satisfaction with the diaper dermatitis treatment used, as measured by the parent satisfaction survey.

The study outcomes will be collected for all participants and comparisons will be made between the two study arms.

Data Collection

Every Diaper Change

The nursing staff or Clinical Research Coordinator in the Genesis NICU will collect information about diaper dermatitis at every diaper change using the diaper dermatitis log. The following information will be included in the log:

1. Date
2. Time
3. Presence of pink or red skin¹¹
4. Presence of pimply areas on the skin.¹¹
5. Presence of eroded and/or blistered skin with bleeding (primary safety endpoint)¹¹

Discharge

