The Clinical Research Coordinator or nursing staff in the Genesis NICU will distribute the Parent Satisfaction Survey to the parent(s). The Parent Satisfaction Survey will include the following questions:

1. How satisfied were you with your baby's participation in this study?
 - 5 - Very satisfied
 - 4 - Satisfied
 - 3 - Neither satisfied nor dissatisfied
 - 2 - Dissatisfied
 - 1 - Very Dissatisfied
2. How satisfied were you with the diaper rash treatment your baby received?
 - 5 - Very satisfied
 - 4 - Satisfied
 - 3 - Neither satisfied nor dissatisfied
 - 2 - Dissatisfied
 - 1 - Very Dissatisfied
3. How would you rate the quality of the diaper rash treatment your baby was given?
 - 5 - Excellent
 - 4 - Very good
 - 3 - Good
 - 2 - Fair
 - 1 - Poor
4. How effective was the diaper rash treatment at preventing diaper rash for your baby?
 - 5 - Very effective
 - 4 - Somewhat effective
 - 3 - Average
 - 2 - Somewhat ineffective
 - 1 - Very ineffective

5. How effective was the diaper rash treatment at treating diaper rash for your baby?
 - 5 - Very effective
 - 4 - Somewhat effective
 - 3 - Average
 - 2 - Somewhat ineffective
 - 1 - Very ineffective
 - Not applicable – My baby did not get diaper rash
6. How likely are you to use the same diaper rash treatment you received at Genesis at home?
 - 5 - Very likely
 - 4 - Somewhat likely
 - 3 - Undecided
 - 2 - Somewhat unlikely
 - 1 - Very unlikely
7. What did you like about your baby’s diaper rash treatment?
8. What could we have done better for your baby’s diaper rash treatment?

Additional Data Variables

Once the study recruitment goal is met, medical record data will be pulled for each participant. The data collected from the medical record will include all data listed in the table below.

Table One: Data Collection Variables

Variable	Source	Definition
Patient Name	Cerner Powerchart	Patient’s first name, middle initial and last name
Age	Cerner Powerchart	Day of life
Race/Ethnicity	Cerner Powerchart	Documentation of the patients self-identified race and ethnicity
Gender	Cerner Powerchart	Male or Female
Height	Cerner Powerchart	Height in inches at start of study
Weight	Cerner Powerchart	Total body weight (kilograms) at start of study
Length of Stay	Cerner Powerchart	Total days during inpatient hospitalization
Medical History	Cerner Powerchart	Diagnosis, reason for admission, allergies, family history
Major Comorbidities	Cerner Powerchart	Documentation of the patient’s major medical conditions

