Expected	Any adverse event that is identified in nature, severity or frequency in the study protocol. Any adverse event that is previously known or anticipated to result from the underlying disease, disorder, or condition of the subject(s).
Unexpected	Any adverse event occurring in one or more subjects participating in the study, the nature, severity, or frequency of which is not consistent with either: 
 1. The known or foreseeable risks associated with the study procedures that are described in the protocol 2. The expected natural progression of any underlying disease, disorder, or condition of the subject(s) experiencing the adverse event and the subject's predisposing risk factor profile for the adverse event.

The Clinical Research Coordinator will assess adverse events on a weekly basis for this study by reviewing patient medical records. Serious adverse events will also be identified by nursing staff on the NICU and will be reported to the Clinical Research Coordinator. The Clinical Research Coordinator will report SAEs to [name] (Principal Investigator) to determine the need for additional treatment. Adverse events that meet the criteria outlined by the Genesis IRB (i.e., events that are unanticipated, serious or anticipated that occur with greater frequency or severity than expected) will be reported to the Genesis IRB within 10 working days after becoming aware of the information, as per Genesis IRB Standard Operating Procedures.

Data Analysis

Once data is transferred to the GHS Biostatistics Group, research team members will double enter the data and manage the databases, assign identification numbers to participants, perform edit diagnostics and prepare worksheets for analysis.

Comparative analyses of Coconut Oil and Standard of Care groups will include exact tests for comparing binomial characteristics, stochastic ordering for ordinal distributions (exact

permutation tests) and Wilcoxon rank sum tests for continuous factors. All will be analyzed with Cytel Studio StatXact Analyses.

Initially, data will be presented as a Kaplan-Meier plot of time to rash for the log-rank comparison of standard treatment and coconut oil. This will provide the probability of rash by treatment on any given day after the start of the study.

Cox proportional analyses will be used to control for risk factors to determine whether they are effect modifiers or confounders of the treatment effect.

Data Management

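### Rash duration and days to erosion (Outcomes 3 and 4) have no named test, no censoring rule and no analysis rule for erosion exit; analysed as raw day counts, they would lose much of their information

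*Protocol*

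**What the plan says.** Study Outcomes is worded identically in both documents. Outcome 3 is "For participants that develop diaper dermatitis, the number of days with diaper dermatitis (duration of diaper dermatitis". Outcome 4, restricted to the same babies, is "the number of days until the participant reaches the primary endpoint (skin eroded and/or blistered with bleeding"; the day from which it is counted is not given.

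Two things end observation. Under Study Procedure, coconut oil babies with rash "will continue to use coconut oil until they are discharged or reach the primary safety endpoint". For either arm, "If a participant reaches the primary safety endpoint their study participation will be complete".

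Data Analysis, also identical in both documents, assigns tests by type of data, including "Wilcoxon rank sum tests for continuous factors". It links the Kaplan-Meier plot and log-rank test to time to rash, and mentions Cox models for risk factors without naming an outcome. The only censoring statement is in the sample-size simulation and concerns rash onset: "Patients that were discharged before getting diaper dermatitis were censored".

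The exclusion criteria remove "Active dermatological conditions other than diaper dermatitis that may affect trial results", so a baby who already has diaper dermatitis can enter.

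**The concern.** Outcomes 3 and 4 are the log-based measures of the treatment half of the trial's question. Each is cut short by events that have nothing to do with healing, and the plan does not say how to handle this. An analyst would have to choose, with the data in view, whether to count an open rash as it stands, drop it or censor it.

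If observed days go into the generic Wilcoxon test, a baby sent home on day 2 of a continuing rash looks the same as a baby healed on day 2. A rash that ends because the skin eroded also looks short. For Outcome 4, babies who heal or go home without erosion have no value, so the comparison shrinks to those who eroded.

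Both outcomes also condition on developing rash, which happens after randomisation and which treatment is meant to change. For babies with rash at entry, the start of the rash is not observed.

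**Working it through.** **Inputs from the Protocol (Participant Selection and Recruitment).** 75 babies per arm; time to discharge C from Gamma(3,2); time to rash T from Gamma(2,2) for coconut oil and Gamma(3,2) for standard care. The parameter order is not stated, so two readings were run: shape first (2,2)/(3,2)/(3,2), and scale first, which as (shape, scale) is (2,2)/(2,3)/(2,3), in the order coconut/standard/discharge. The arm order is the Protocol's own.

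**Assumed, because neither document gives them.** True rash duration D is gamma with shape 2 and mean 3 or 6 days. Time from rash to erosion E is exponential with the hazards shown below. There is one rash per baby, erosion is independent of duration, time is in days and tests are two-sided at 5%.

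**1. The plan's own figure.** The Protocol reports p = 0.002 for 75 per arm, for time to rash only. It is a single simulated p-value, so it can be judged only for plausibility. The figure's caption (shape 2, scale 2 vs 3) gives median p 0.0046 and power 0.80. The text read shape first gives median p 0.00045 and power 0.94. The stated value is plausible under both, but says nothing about Outcomes 3 and 4.

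**2. Babies available.** A baby contributes if T ≤ C. Shape first: 0.688 × 75 ≈ 52 coconut and 0.501 × 75 ≈ 38 standard. Scale first: 0.649 × 75 ≈ 49 and 0.501 × 75 ≈ 38.

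**3. Outcome 3, no erosion.** Observed days = min(D, C − T, E). A rash is open at discharge if C − T is the smallest.

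- Open at discharge: about 40–45% at a true mean of 3 days, 61–68% at 6 days.
- A true difference of 4.5 − 3 = 1.5 days appears as 0.3–0.7 day, that is 0.3/1.5 = 20% to 0.7/1.5 = 47% of it.
- Power for that difference: about 11–38% by Wilcoxon on observed days, 48–54% by log-rank with open rashes censored.
- With exponential durations instead (2 vs 4 days, caption parameters): 37% against 71%.

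**4. Outcome 3, direction.** True durations equal; the nominal rate in one direction is 2.5%.

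| Erosion hazard per rash-day, coconut vs standard | Rash babies who erode | Wilcoxon calls coconut shorter |
|---|---|---|
| none | none | 0.5–2% |
| 0.02 vs 0.01 | 4–6% vs 2–3% | 1–2% |
| 0.10 vs 0.05 | 18–25% vs 9–13% | 3–7% |
| 0.20 vs 0.05 | 31–41% vs 9–13% | 14–29% |

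With no erosion, unequal onset alone tilts Wilcoxon modestly the other way (standard shorter in 4–8%). At 0.20 vs 0.05, log-rank censored at erosion exit rejects in 2–4% each way. That good behaviour depends on the assumed independence of erosion and duration.

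**5. Outcome 4.** At 0.02 vs 0.01 about 2–3 vs 1 babies have a value, and in roughly 37–54% of simulated trials one or both arms have none. A Poisson hand check uses P = 1 − (1 − e^−a)(1 − e^−b), where a and b are the expected eroders per arm:

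- a = 52 × 0.04 = 2.08, b = 38 × 0.02 = 0.76: P = 1 − 0.875 × 0.532 = 0.53.
- a = 52 × 0.06 = 3.12, b = 38 × 0.03 = 1.14: P = 1 − 0.956 × 0.680 = 0.35.

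At 0.20 vs 0.05, Wilcoxon among eroders rejects in 4–7% of trials. Log-rank in the same rash population, with non-eroders censored, rejects in about 70–86%. Wilcoxon sees only the timing among those who eroded and discards how many did.

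**The case against.** The plan is silent rather than committed to Wilcoxon. Outcome 1 is also worded as a number of days, yet it receives Kaplan-Meier and log-rank; Outcome 4 is worded as a time to an event; and the Cox sentence names no outcome. The sponsor may intend survival methods throughout. This stands as a limit on the claim: the consequences above follow only if observed days are analysed as they are. It does not close the gap, because neither document extends log-rank or censoring beyond time to rash.

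Outcome 3 may mean days with rash while in the NICU, which a log kept at every diaper change supports. Discharge then does not truncate the count. The count still depends on length of stay and still needs an erosion rule, and the documents do not say which meaning is intended.

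A reader might infer that there is no erosion-exit rule at all. There is: participation ends. Only its handling in the analysis is missing.

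A reader might also infer that the plan would make coconut oil look better by hiding harm. The documents do not support that. They give no erosion rates, and at low hazards Wilcoxon's rate of calling coconut shorter is at or below nominal. A large excess of erosions would still appear in the safety data and to the Data and Safety Monitoring Board.

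Conditioning on rash is inherent in asking about treatment of rash; it calls for a label and cannot be removed. How common rash at entry would be is unknown, and such a baby arguably did not develop it on study.

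**Conclusion.** The point holds and should be fixed before analysis, in proportion to two secondary outcomes. The test, time origin, censoring rule and analysis of erosion exit are unspecified. Under the stated assumptions, raw day counts cut Outcome 3 power from about 48–54% to 11–38% for a 1.5-day difference and under-count duration. Material directional bias arises only if erosion is frequent and unequal between arms. For Outcome 4, raw counts can leave an arm with no data when erosion is rare, and discard most of the information when it is common.

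Durations and erosion hazards are assumed throughout; only onset, discharge and sample size come from the Protocol.

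A stronger contrast for Outcome 4 is tempting: at 0.20 vs 0.05, log-rank in all randomised babies rejects in about 88–98% of trials. That is not a like-for-like comparison. It changes population and time origin as well as test, and in the Protocol's own simulation coconut oil also has the earlier rash. At 0.10 vs 0.05 (mean 3 days) it gives 35–42%, against 16–18% within rash babies, so over half of it reflects rash onset and not progression.

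**What to change.** Add to the SAP:

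- **Outcome 3.** Analyse time from first logged rash to resolution (defined from the logged signs) by Kaplan-Meier and log-rank, censoring open rashes at discharge and at erosion exit. Report it beside the number of erosions by arm, because erosion exit is informative. As a sensitivity analysis, treat erosion as a competing event with those babies kept unresolved. Report raw in-NICU rash-days descriptively.
- **Outcome 4.** Analyse time from first rash to erosion by Kaplan-Meier and log-rank in rash babies, censoring those who do not erode at discharge. Add time from randomisation to erosion in all randomised babies as a comparison free of conditioning on rash, and state that it includes any effect through rash onset.
- **Both.** Label the rash-only comparisons supportive, and state how rash present at entry is handled.

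Making the competing-event analysis the main test for Outcome 3 is optional and debatable. With equal true durations at 0.20 vs 0.05 it rejected against the eroding arm in 29–37% of trials, so it tests a mixture of duration and erosion. Replacing Outcome 4 by the all-randomised analysis is likewise optional.

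The cost is SAP wording and a little programming. No new data are needed: the log is dated and timed at each diaper change, and Table One collects length of stay, "Total days during inpatient hospitalization". The downside is that Outcome 3 moves from a raw day count to time to resolution, and the rash-only comparisons still condition on a post-randomisation event.

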Studies have shown that coconut oil can be absorbed through the skin of neonates, without any negative side effects.^{7,8} One randomized, controlled study found preterm babies massaged with coconut oil daily for 31 days had significantly higher weight gain velocity compared to mineral oil and placebo, and higher length gain velocity compared to placebo.⁸ Other studies have found coconut oil to be an effective treatment for atopic dermatitis in pediatric and adult patients. One randomized controlled trial of 117 pediatric patients found topical application of virgin coconut oil for eight weeks was superior to that of mineral oil based on clinical (SCORing of Atopic Dermatitis [SCORAD]) and instrumental (transepidermal water loss [TEWL], skin capacitance) assessments.⁹ Another double-blind controlled trial of 52 adults found virgin coconut oil was significantly more effective than virgin olive oil at reducing the prevalence of *Staphylococcus aureus* (RR=0.10, p=0.0028), indicating coconut oil may have an antimicrobial effect.¹⁰

Purpose/Objectives

The purpose of the study is to examine the safety and effectiveness of the use of coconut oil for the prevention and treatment of diaper dermatitis among NICU babies at Genesis Medical Center, Davenport.

Primary objectives:

1. To determine and compare the number of days free of diaper dermatitis (“time to rash”) within and between the two treatment groups (i.e., coconut oil and standard of care)
2. To identify the adverse effects of coconut oil when used as a barrier cream for the prevention and treatment of diaper dermatitis

Secondary objectives:

3. To determine and compare the duration of diaper dermatitis within and between the two treatment groups.
4. To determine and compare changes in diaper dermatitis severity within and between the two treatment groups.
5. To determine and compare parent satisfaction scores within and between the two treatment groups at discharge.

[figure not shown]
Study Design

This is a prospective, randomized controlled trial to examine the effect of coconut oil on the prevention and treatment of diaper dermatitis in NICU babies at Genesis Medical Center, Davenport. The study will be carried out in the Genesis Medical Center, Davenport NICU. The

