## Introduction/Background

Diaper dermatitis is an inflammatory reaction of the skin in the perineal area of infants, and is a common pediatric condition. It can have many causes including infection (yeast, bacterial or viral), friction irritation, skin sensitivity to urine and/or feces, and allergies (perfumes). The overall incidence of diaper dermatitis in infants is estimated to be between 7% and 35%. Diaper dermatitis is often a result of increased moisture due to contact with urine and feces, followed by friction. Urine contact with diapered skin raises the skin pH, thus increasing skin permeability and activating fecal enzymes, which are known irritants that can cause skin breakdown. Skin breakdown encourages secondary skin infections that increases the challenge of managing diaper dermatitis. Diaper dermatitis can range in severity from generalized erythema (redness of the skin) to open wounds, and can cause significant pain for babies and distress for parents.

Premature infants have been found to be at higher risk for diaper dermatitis due to their age, and varying degrees of underdeveloped skin structures and functions. In addition, babies that are ill have a higher risk due to increased incidence of diarrhea, cancer, gastrointestinal anomalies, neurological disorders, genetic syndromes and malnutrition. Genesis Neonatal Intensive Care Unit (NICU) infants are often on a number of antibiotics that cause diarrhea, which significantly contributes to the challenges Genesis faces with diaper dermatitis. Genesis estimates its incidence of diaper dermatitis in the NICU is approximately 50%.

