Participants in each arm will be cleaned with the same Pampers Sensitive brand wipes and will receive the same Pampers brand disposable diaper. The Coconut Oil group will receive coconut oil at each diaper change. An individual sterilized container of unrefined, organic coconut oil will be placed in the participant's room. The coconut oil will be obtained from a large jar and will be placed into the individual sterilized container at the time of randomization. The coconut oil will be labeled with the participant's name and date of birth. At each diaper change participants will be cleaned with Pampers brand wipes and a generous layer of coconut oil will be applied to the diaper area, including buttocks and creases between thighs and hips. Participants in the Coconut Oil group that develop diaper dermatitis will continue to use coconut oil until they are discharged or reach the primary safety endpoint. They will also be switched from using Pampers Sensitive wipes to a dry washcloth and water, per the standard of care.

The Standard of Care group will receive the current standard of care for diaper dermatitis. The standard of care is no treatment until a diaper dermatitis appears. If diaper dermatitis appears, participants will receive a generous layer of Medline Remedy Phytoplex Z-Guard Skin

Protectant, which is an over-the-counter skin protectant with the following active ingredients: white petrolatum 57% and zinc oxide 17%. The participants will also be switched from using Pampers Sensitive wipes to a dry washcloth and water, per the standard of care.

The primary safety endpoint for this study will be skin that is eroded and/or blistered in the diaper area with bleeding. If a participant reaches the primary safety endpoint their study participation will be complete and additional diaper dermatitis treatment options can be used, per currently available treatment options in the Genesis NICU.

The research staff will conduct a quality check each week using a sample of participant rooms to ensure the participants continue to receive care based on the study arm they were assigned to and the diaper dermatitis logs are being completed for every diaper change.

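### The diaper dermatitis log has no separate entry for eroded or blistered skin that is not bleeding, so the log-based severity comparison misses that stage

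*Protocol*

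**What the plan says.** The Protocol (Data Collection, Every Diaper Change) lists the contents of the log: date, time and three skin signs. The signs are "Presence of pink or red skin", "Presence of pimply areas on the skin" and "Presence of eroded and/or blistered skin with bleeding (primary safety endpoint". The SAP gives the same list under the same heading.

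The Study Procedure section of both documents defines the endpoint that the third sign serves: "The primary safety endpoint for this study will be skin that is eroded and/or blistered in the diaper area with bleeding". Reaching it ends the baby's participation.

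Secondary objective 4 in both documents is "To determine and compare changes in diaper dermatitis severity within and between the two treatment groups". In Study Outcomes, the only entry that corresponds to it is secondary outcome 4, for babies who develop a rash: "the number of days until the participant reaches the primary endpoint (skin eroded and/or blistered with bleeding), as measured by the diaper dermatitis log".

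The SAP's Introduction/Background describes the condition more broadly: "Diaper dermatitis can range in severity from generalized erythema (redness of the skin) to open wounds". Bleeding is not part of that description.

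**The concern.** The log is the only skin record made at each diaper change, and its list goes from pimply skin directly to breakdown with bleeding. Skin that has opened or blistered but does not bleed lies between the two. By the SAP's own account of severity it belongs towards the severe end, yet the log does not distinguish it.

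Two things are at stake. First, objective 4 asks about change in severity, but its only outcome registers the last step. A difference between arms in non-bleeding breakdown would not appear in it unless the breakdown went on to bleed. Second, anyone monitoring skin harm from the log would see bleeding breakdown without a distinct record of the stage before it. The staff completing the log can know the arm, because the product is placed in the room and the charge nurse is told the allocation (Study Procedure). Unguided choices about how to tick such skin could therefore differ by arm.

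**Working it through.** The claim concerns which skin states the log can hold. The plan has no figure to reproduce, so the main check sets the sections side by side.

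**Step 1. Skin state against log entry (Data Collection, Every Diaper Change, both documents).**

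| Skin state | Log entry |
|---|---|
| Red | Item 3 |
| Pimply | Item 4 |
| Eroded or blistered, not bleeding | None of its own; no rule for items 3 and 4 |
| Eroded or blistered, bleeding | Item 5 |

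**Step 2. Objective against outcome.** Objective 4 (severity) maps to secondary outcome 4 (days to the bleeding endpoint). Outcome 1 (days free of rash) and outcome 3 (days with rash) measure presence and duration, not grade.

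**Step 3. Other sources.** Table One (Additional Data Variables) lists no skin grade. The Risks section tracks rash that worsens and skin that becomes inflamed or swollen. Safety Reporting defines an adverse event broadly, with no bleeding condition, and has the coordinator review charts weekly. Neither section contains an erosion criterion. The moderate grade is set by the intervention needed. In the standard arm any rash triggers the barrier product, while in the coconut arm the oil simply continues. The grade could therefore reflect the arm's treatment rule rather than the lesion.

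**Step 4. Possible reach into outcome 1.** If non-bleeding breakdown were ticked as neither red nor pimply, that diaper change could be read as rash-free. The documents do not exclude this. Broken skin will presumably often be red as well, so this is a possibility and not an expectation.

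**Step 5. Size, by illustration only.** From the documents: 75 babies per arm (Protocol, Participant Selection and Recruitment) and a unit incidence of about 50% (SAP, Introduction/Background). Every other input is assumed.

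- Rashes per arm: 0.50 × 75 = 37.5.
- If 10–30% erode: 37.5 × 0.10 = 3.75 to 37.5 × 0.30 = 11.25.
- If 25–75% of those never bleed: 3.75 × 0.25 = 0.9 to 11.25 × 0.75 = 8.4 babies per arm with breakdown that has no entry of its own.

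A second, wider set of assumptions shows what counting only bleeding breakdown does to a comparison of proportions. Erosion occurs in 10% or 40% of control-arm rashes and is twice as frequent in the other arm; two-sided alpha is 0.05. With n = 75 per arm and p̄ the mean of p₁ and p₂,

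power = Φ{[|p₂ − p₁| − 1.96√(2p̄(1 − p̄)/n)] / √([p₁(1 − p₁) + p₂(1 − p₂)]/n)}.

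For 10% erosion, p₁ = 0.50 × 0.10 = 0.05, p₂ = 0.10 and p̄ = 0.075. This gives (0.05 − 1.96 × 0.0430)/0.0428 = −0.80, so power is 0.21.

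| Control rashes eroding | Share of eroded that bleed | Eroded, expected | Power, any erosion | Bleeding, expected | Power, bleeding only |
|---|---|---|---|---|---|
| 10% | 10% | 3.8 vs 7.5 | 0.21 | 0.4 vs 0.8 | 0.05 |
| 10% | 50% | 3.8 vs 7.5 | 0.21 | 1.9 vs 3.8 | 0.12 |
| 40% | 10% | 15 vs 30 | 0.77 | 1.5 vs 3.0 | 0.11 |
| 40% | 50% | 15 vs 30 | 0.77 | 7.5 vs 15 | 0.40 |
| 40% | 100% | 15 vs 30 | 0.77 | 15 vs 30 | 0.77 |

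The normal approximation is rough at the smallest counts. The table shows direction: less information whenever a fair share of erosions do not bleed, and no loss if all do.

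**The case against.** The strongest reply is that harm is not monitored through the log alone. The number of babies with adverse effects is itself a primary outcome. Worsening rash is a tracked risk, any untoward sign counts as an adverse event, events are graded, charts are read weekly, and a Data and Safety Monitoring Board reviews events and study data. This stands. A reader might infer that the trial cannot see harm before bleeding, and the documents do not support that. What remains is that this route is slower, depends on what is charted and does not ask about erosion. For the same reason, later recovery from the chart is uncertain but not ruled out.

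Other stronger readings also fail:

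- **That such skin is recorded as simple redness.** The documents list the log's contents but do not include the form or its completion instructions. The skin could be ticked red, pimply, both or neither. The three items cite a published study of an ointment for diaper dermatitis; whether that source settles the scoring cannot be checked here.
- **That severe rash cannot be measured.** Bleeding breakdown is captured, and three signs give a coarse ordering.
- **That a product causing more non-bleeding breakdown would look equal on every log outcome.** Rash-free days, rash duration and time to bleeding could each still differ.
- **That item 5 is ambiguous, with erosion alone enough to tick it.** The endpoint definition, "skin that is eroded and/or blistered in the diaper area with bleeding", puts the location between the pair of signs and the bleeding condition. The natural reading is that bleeding applies to both signs.

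It is also fair that the bleeding threshold is a stated choice for the safety endpoint. The point here leaves that threshold alone and concerns only what is recorded below it.

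**Conclusion.** The point holds in a limited form. As listed in both documents, the log does not separately record eroded or blistered skin without bleeding, and the severity objective is served only by time to the bleeding endpoint. The log-based severity comparison and log-based harm detection therefore miss one stage, leaving non-specific weekly adverse-event review to find it.

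The effect falls mainly on a secondary objective. The planned time-to-rash comparison is touched only if such skin were ticked as neither red nor pimply. The size is unknown, because the documents give neither an erosion rate nor the share of erosions that bleed. The figure of roughly 1 to 8 babies per arm rests wholly on assumed ranges for both and should not be read as an estimate. The change is worth making because it is cheap and because the information is most reliably captured at the diaper change itself.

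**What to change.** 1. In Data Collection (Protocol and SAP), split log item 5 into two yes/no boxes: 5a, eroded or blistered skin; 5b, bleeding. Derive the safety endpoint from the two boxes exactly as Study Procedure already words it.
2. State how items 3 and 4 are ticked when 5a is ticked, so that no such diaper change can be read as rash-free by default.
3. Add an outcome under objective 4, reported by arm for all randomised babies: any skin breakdown (5a ever ticked), and the worst log stage reached (none, red, pimply, eroded or blistered, eroded or blistered with bleeding). The exact permutation test for ordinal distributions and the exact test for binomial characteristics already named in Data Analysis can be used.

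The cost is one more tick box at each diaper change, a few lines in the two documents and one more secondary analysis. This is a recording and reporting change only. No change to treatment or to the stopping rule is proposed.
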